9.3. Variables

The study will collect all relevant data including patient demographics (e.g., age and sex), comorbidities, prescription medications, vaccinations, procedures, and laboratory tests prior to initiating abrocitinib and while on treatment to address the study objectives. Abrocitinib and concomitant medications and vaccinations will be identified using ATC codes. Diagnoses will be recorded using diagnostic codes. Performance of laboratory tests, available from Denmark, will be identified using Nomenclature, Properties and Units (NPU) codes. Surgeries will be defined using country-specific procedure/surgery codes. Age (date of birth) and sex will be used as reported in the databases. The average daily dose of abrocitinib will be estimated using a combination of information available per country: strength of the prescription dispensed, packet size, World Health Organization (WHO) defined daily dose and duration of therapy (time between prescriptions/dispensings). Availability of specific data types varies by country. There is no information in Hungary available to estimate dose therefore this data source will not be included in analyses of dose.

The maximum lookback period for ascertaining characteristics before abrocitinib initiation will be 12 months (365 days), but will vary for a given RMM measure, per SmPC. Full country-specific algorithms for all study variables, including RMM-specific lookbacks will be specified in the SAP.

Table 1 summarizes the data available by country for analysis of patient co-morbidities, and prior and current medication use. Table 2 summarizes types of RMMs and specificity available by country for analysis. ANNEX 3. ADDITIONAL INFORMATION provides preliminary definitions of the codes to be used to define each element, per country.

Table 1. Availability of patient co-morbidities and concomitant medications in each country

	Denmark	France	Sweden	Spain 1	Hungary
Co-morbidities					
Acne	No	No	No	Yes	Yes
Allergic conjunctivitis	No	No	No	Yes	Yes

	Denmark	France	Sweden	Spain	Hungary
Allergic rhinitis	No	No	No	Yes	Yes
Anxiety	If treated in specialist care or through medication	No (unless hospitalized)	If treated in specialist care or through medication	Yes	Yes
Asthma	Identification of persisting asthma using hospital records and medication is possible.	Identification of persisting asthma using hospital records and medication is possible.	Yes	Yes	Yes

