²Cyclosporine, azathioprine, methotrexate, mycophenolic acid, mycophenolate mofetil, dupilumab, tralokinumab; other treatments authorized per country at the time of analysis

³Arbamazepine, rifabutin, enzalutamide, letermovir, phenytoin, rifampicin, apalutamide, rifamycin, rifaximin, rifapentine, bosentan, alpelisib, dabrafenib, efavirenz, fluconazole, flucoxetine, fluvoxamine, ticlopidine

RMM element	Denmark	France	Sweden	Spain ¹	Hungary ^{1, 2}
Complete blood count: absolute lymphocyte count, absolute neutrophil count, platelet count and haemoglobin level	Yes (date performed, hospital labs)	Yes (in/outpatient lab test, no results)	No	Yes if conducted in primary care	Yes (in/outpatient lab test, no results)
Lipid panel: total cholesterol, high- density lipoprotein [HDL], low- density lipoprotein [LDL], and triglycerides [TG])	Yes (date performed, hospital labs)	Yes (in/outpatient lab test, no results)	No	Yes if conducted in primary care	Yes (in/outpatient lab test, no results)
Hepatitis B screening	No	Yes (in/outpatient lab test, no results)	No	No	Yes (in/outpatient lab test, no results)
Hepatitis C screening	No	Yes (in/outpatient lab test, no results)	No	No	Yes (in/outpatient lab test, no results)
TB screening	No	Yes (in/outpatient	No	No	Yes (in/outpatient

 Table 2.
 Availability of RMM elements for evaluation in each country

PFIZER CONFIDENTIAL

RMM element	Denmark	France	Sweden	Spain ¹	Hungary ^{1, 2}
		lab test, no results) or ATC codes (tuberculin skin test)			lab test, no results)
Risk factors for VTE, MACE, malignancy excluding NMSC, NMSC, and serious infection:					
History of VTE	Yes, via in/outpatient diagnoses	Yes, via inpatient diagnoses and outpatients algorithm previously used and validated in a PASS study	Yes, via in/outpatient diagnoses	Yes if recorded in primary care	Yes
Age 65 years or older	Yes	Yes	Yes	Yes	Yes
Dose of > 100 mg/day for patients 65 or older	Yes ³	Yes ³	Yes ³	Yes ⁴	No
History of atherosclerotic disease	Yes, in/outpatient diagnoses	Yes, via inpatient diagnoses and Long term disease registration	Yes, via in/outpatient diagnoses	Yes if recorded in primary care	Yes
Malignancy excluding NMSC, NMSC	Yes, via Danish Cancer Registry or Danish Cancer Registry	Yes, via Long Term Disease registration status, inpatient diagnosis and outpatients treatments for prostatic cancer	Yes, via Swedish Cancer Register	Yes if recorded in primary care	Yes

Table 2. Availability of RMM elements for evaluation in each country

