9.7. Data Analysis

9.7.1. Main analyses

Detailed methodology for summary and statistical analyses of data collected in this study will be documented in the SAP, which will be dated, filed, and maintained by the sponsor. The SAP may modify the plans outlined in the protocol; any major modifications would be reflected in a protocol amendment.

Data will be analysed in each country separately using a common protocol, database-specific definitions of the study variable, and common analysis strategies. Only data available in a given country will be analysed and presented (Table 1,Table 2). The results will be presented separately for each country.

For each country, patient baseline characteristics will be reported to the extent measured in each database, including demographics (age and sex), comorbidities (including asthma, food allergies, depression) and prior and current medication use (including treatments for atopic dermatitis and medications noted for interactions in the abrocitinib label as captured in outpatient dispensing data or other available secondary routinely collected data on medication use). Other characteristics frequently diagnosed among patients with atopic dermatitis may be added given acceptable validity and completeness measured via diagnoses or treatment proxies and known in time for inclusion in planned data extractions; existing

PFIZER CONFIDENTIAL

ethical and data protection permissions and the associated data applications may need to be amended to enable inclusion of additional variables.

Counts and proportions for categorical variables and mean, median with range or interquartile ranges (IQRs) for continuous variables will be reported to address the study objectives, as follows:

1) The count and proportion of patients with evidence of having performed the following laboratory tests and screenings within 3 months prior to initiation of abrocitinib:

- CBC including absolute lymphocyte count, absolute neutrophil count, platelet count and haemoglobin level
- Lipid panel (ie, total cholesterol, HDL, LDL, and TG)
- Screening for TB, and
- Screening for viral hepatitis B and C

2) The count and proportion of patients with evidence of having performed the following laboratory tests at week 4 (\pm 2 weeks) after initiation of abrocitinib:

- CBC including absolute lymphocyte count, neutrophil count, platelet count and haemoglobin level
- Lipid panel (i.e., total cholesterol, HDL, LDL, and TG)

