17. ANNEX 3. ADDITIONAL INFORMATION

Annex 3 Table A1: Preliminary variable definitions in each database (subject to refinement in the SAP)

Variable definitions for data from Spain (SIDIAP) and Hungary (NHIFA) will be included in the SAP.

RMM element	Denmark	France	Sweden
Complete blood count: absolute lymphocyte count, absolute neutrophil count, platelet count and haemoglobin level	Potential candidate example codes (subject to refinement): NPU codes NPU01960 B— Erythrocytes NPU02902 B— Neutrophilocytes; NPU02636 B— Lymphocytes; num.c. NPU02319 B— Haemoglobin(Fe); NPU02322 P— Haemoglobin(Fe); NPU027411 P— Haemoglobin NPU03568 B— Thrombocytes	Complete blood count including platelets: TNB code 1104	No
Lipid panel total cholesterol, HDL, LDL, and TG	Potential candidate example codes (subject to refinement) NPU codes total cholesterol: NPU01566, NPU18412 High-density lipoprotein: NPU01567, NPU10157, low-density lipoprotein: AAB00101-102, NPU01568, NPU10171, Triglycerides: NPU03620, NPU04094	TNB codes: total cholesterol: 0580, TG: 0590, c-LDL: 2001, exploration of lipid abnormality: 0996 (test only, no result)	No
Hepatitis B screening	No	TNB codes: Hepatitis B screening: 4500, screening IgM anti-HVC: 4501	No
Hepatitis C screening	No	TNB codes: Quantitative genome (RNA) detection: 4124, genotyping HVC: 4125	No
TB screening	No	TNB code: 0243 (test only, no result)	No

PFIZER CONFIDENTIAL

CT24-WI-GL02-RF02 3.0 Non-Interventional Study Protocol Template For Secondary Data Collection Study 20-May-2021 Page 46

RMM element	Denmark	France	Sweden
Risk factors for VTE, MACE, malignancy and serious infection:			
History of VTE	ICD-10 codes I26, I82.0, I82.2; I82.3, I82.8, I82.9	ICD-10 codes I26, I82.0, I82.2; I82.3, I82.8, I82.9	ICD-10 codes I26, I82.0, I82.2; I82.3, I82.8, I82.9
History of atherosclerotic disease	ICD I70.0 – I70.9	ICD10 code I70	ICD10 code I70
Malignancy	ICD-10 codes C00-C75, C81-C96	ICD-10 codes C00-C75, C81-C96; treatment proxy if relevant	ICD-10 codes C00-C75, C81-C96

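### French hepatitis code rows in Annex 3 are internally inconsistent: the hepatitis C row has no test labelled as screening, and a test labelled anti-HVC sits under hepatitis B

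*Protocol*

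**What the plan says.** Section 9.7.1, main analysis 1, reports the count and proportion of patients with evidence of "laboratory tests and screenings within 3 months prior to initiation of abrocitinib". One of the listed items is "Screening for viral hepatitis B and C".

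Section 9.3 says that Annex 3 "provides preliminary definitions of the codes to be used to define each element, per country". The French column of Annex 3 Table A1 gives:

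- Hepatitis B row: "TNB codes: Hepatitis B screening: 4500, screening IgM anti-HVC: 4501".
- Hepatitis C row: "TNB codes: Quantitative genome (RNA) detection: 4124, genotyping HVC: 4125".
- TB row: "TNB code: 0243 (test only, no result", the only entry there.

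Table 2 in Section 9.3 describes French TB screening more widely, as a laboratory test "or ATC codes (tuberculin skin test". It marks hepatitis B, hepatitis C and TB screening as available in France and Hungary only, with tests recorded but not their results. Annex 3 leaves the Hungarian definitions to the SAP.

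The table title gives its status: "Preliminary variable definitions in each database (subject to refinement in the SAP".

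**The concern.** The indicator is meant to show whether prescribers had patients screened before treatment. RNA quantification and genotyping mainly serve to measure or characterise an infection that is already known or suspected. Most patients who are screened and found negative would have neither. A definition made up only of these two tests leaves such patients out of the numerator, although they were managed as the risk minimisation measures ask.

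The annex uses HVC for hepatitis C in the hepatitis C row. By its own labels, then, a hepatitis C antibody screen stands in the hepatitis B row. At stake is a French result that suggests prescribers are not screening for hepatitis C when the code list is not counting the screen. The Hungarian definitions are still to come, so the French cells are the only definitions of these screenings that the protocol states.

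**Working it through.** **1. The plan's own figure.** Section 9.5 uses n = P(1−P)·Z²/e². With P = 0.50, e = 0.05 and Z = 1.96, n = 0.25 × 3.8415 / 0.0025 = 384.15, rounded up to 385. All nine entries of Table 3 reproduce. The arithmetic is not in question. The issue is what the numerator counts.

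**2. The rows on either reading of 4501.**

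| | 4501 is a hepatitis C antibody test | 4501 is a hepatitis B marker with a misprinted label |
|---|---|---|
| Hepatitis C row | Its screening test is in the other row | No screening test is listed for hepatitis C |
| Hepatitis B row | Can count a patient who had only a hepatitis C test | Sound |

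The hepatitis C row fails in both columns. The hepatitis B row fails in one.

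**3. Size for hepatitis C.** Let s be the true proportion screened and f the share of screened patients who also have RNA quantification or genotyping in the window. Assume that no one has those tests without being screened. Then recorded proportion = s × f. The protocol gives neither s nor f, so both are assumed.

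| f | s = 50% | s = 75% |
|---|---|---|
| 1% | 0.5% | 0.75% |
| 3% | 1.5% | 2.25% |
| 10% | 5.0% | 7.5% |
| 25% | 12.5% | 18.75% |

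The recorded value equals the true one only at f = 100%.

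**4. The confidence interval does not reveal the problem.** Take 385 patients for illustration (the protocol sets no minimum and gives no French count), with s = 75% and f = 25%. Then 385 × 0.75 × 0.25 ≈ 72 patients are counted, or 18.7%, with a 95% Wilson interval of 15.1 to 22.9%. The interval is narrow and far from 75%.

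**5. Size for hepatitis B.** Let b be the true proportion with a hepatitis B test, and c the share with the 4501 test but no hepatitis B test. If 4501 is a hepatitis C test, recorded proportion = b + c. With b = 50% and c = 0, 2, 5, 10 or 20%, this gives 50, 52, 55, 60 or 70%. If 4501 is a hepatitis B marker, the inflation is zero. The protocol gives no value for c.

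**6. TB.** Table 2 names two routes and Annex 3 codes one. Patients screened by skin test alone would be missed. The documents give no share, so no size can be attached.

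**The case against.** The strongest reply is that nothing here is fixed. The table is headed preliminary, Section 9.3 leaves the full country algorithms to the SAP, and the SAP is not at hand. This stands in part: it lowers the severity and makes every consequence conditional on the list going forward unchanged. It does not remove the point, because the cells are stated content that conflicts with itself, not detail left open. Where the annex regards codes as tentative or still in development, as in the Danish laboratory cells and for severe hepatic impairment, it adds its own note. The French hepatitis cells carry none.

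A second reply is Section 9.9, which concedes difficulty in identifying hepatitis and TB screening and limits what an absent record may mean. Those caveats concern under-recording. They do not cover counting a different test, which would mislead even in a complete database.

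A third reply is scope. Hungary also supplies these indicators and results are shown by country, so a French error would not carry over. That stands.

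For TB, the skin-test route is already recognised in Table 2. Its absence from Annex 3 is incompleteness, a lesser matter than a test listed under another virus.

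**Conclusion.** The French hepatitis B and C rows are internally inconsistent and need correcting. If used as written, the French hepatitis C indicator would be biased low: about 0.5 to 2.3% recorded against 50 to 75% true for f of 1 to 3%, and 5 to 19% for f of 10 to 25%. The direction follows from the row's content. The size rests on assumed s and f.

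A reader might go further in three ways that the documents do not support:

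- That the code numbers are wrong. The nomenclature is not in the documents, and the fault may be in a label.
- That hepatitis C adherence would necessarily read near zero. That holds only if RNA testing and genotyping are rare among screened patients, and the protocol gives no rate.
- That hepatitis B adherence is inflated. That needs 4501 to be a hepatitis C test and some patients to have it without a hepatitis B test. The inflation may be nil.

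Severity is moderate: one country's indicators are affected, in a table marked as preliminary. The TB mismatch between Table 2 and Annex 3 is secondary.

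**What to change.** Before data extraction:

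1. Check codes 4500, 4501, 4124 and 4125 against the French laboratory nomenclature and correct the labels.
2. Place each code under the virus that it detects.
3. Define hepatitis C screening by the hepatitis C antibody (serology) code or codes. Do not count genotyping (4125) as screening. RNA quantification (4124) can be kept as supplementary evidence, reported apart.
4. Add the tuberculin skin-test ATC code to the French TB row, so that Annex 3 agrees with Table 2.

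The cost is the correction of three table cells and their counterparts in the SAP. The French laboratory and dispensing data already planned would serve. Timing matters more than effort: Section 9.7.1 notes that additional variables may require amended permissions and data applications, and Section 6 plans the start of data collection for 31 December 2024. Any added code should therefore be confirmed as covered by the French data application before extraction.

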3) The proportion of patients with evidence of having risk factors and the number of risk factors for VTE, MACE, malignancy excluding NMSC, NMSC, and serious infection (including age 65 years or older, estimated dose of >100 mg/day for patients ages 65 or older, history of atherosclerotic disease, malignancy, pregnancy, history of VTE, use of combined hormonal contraceptives or hormone replacement therapy, major surgery, inherited coagulation disorder, diabetes, history of serious or opportunistic infection, TB) within 6 months prior to initiation of treatment with abrocitinib

4) The count and proportion of patients with evidence of having received live attenuated vaccines (e.g., measles, mumps, rubella) 4 weeks prior to and during treatment with abrocitinib

5) The count and proportion (among all pregnant women identifiable in a given database) of women in whom pregnancy overlaps with abrocitinib use

6) The count and proportion patients identified with severe hepatic impairment up to 6 months prior to or during treatment with abrocitinib

7) The count and proportion of patients aged <12 years on the index date

PFIZER CONFIDENTIAL

Abrocitinib B7451085 NON-INTERVENTIONAL STUDY PROTOCOL Version 2.0, 23 May 2024 8) The count of proportion of patients with an estimated starting dose > 100mg/day, and a description of the duration of use (median and IQR)

All proportions will be reported with 95% CIs.

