9.9. Limitations of the Research Methods

Given the use of data sources from 5 distinct EU countries in this study, there will be variability in data captured across the participating countries. For example, data on laboratory tests and vaccinations are not available in Sweden and may be underrecorded in Denmark and France. If only reimbursed services are recorded (e.g., vaccinations, oral contraceptives), some underascertainment will be associated with absence of data on nonreimbursed services. Given the underrecording, absence of a record of a given RMM metric (e.g., hepatitis B, hepatitis C, or TB screening) cannot be interpreted as an indicator of nonadherence for all metrics, and only databases with high completeness of these data should be used in that assessment (Table 2). Similarly, as vaccines recording is based on reimbursement and data is not expected to be complete, the absence of a record is not necessarily indicative of absence of vaccine receipt. Additionally, prescription strength data serves as a proxy for daily dosage in this study; this approach is supported by the absence of scoring on the abrocitinib 200 mg tablets (which would facilitate splitting into separate 100 mg doses), and by reimbursement in Sweden, Denmark, France and Spain (pending for Hungary) for both the 100 mg and 200 mg tablets (i.e. there is no financial justification for a patient to receive a prescription strength of 100 mg to be taken as 2 tablets to achieve 200 mg daily dosage). However, there may be instances where patient dosage does not correspond to the strength prescribed. Dosage data from SIDIAP can only be derived from a combination of WHO Defined Daily Dose (DDD); data from NHIFA on dosage is not available.

Other limitations include uncertainty about identification of abrocitinib in Denmark (however, most newly approved medicines receive hospital procedure codes); incomplete identification of ongoing pregnancies and pregnancies ending in a termination, as they are identifiable only by pregnancy end date; challenges in identifying screening for TB and hepatitis B and C in all participating countries; and potential underestimation of history of atherosclerotic disease given the likelihood of treatment within a primary care setting in all participating countries. Results from participating countries will not necessarily be generalizable to other countries in the EU.

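### Annex 3 identifies history of atherosclerotic disease by ICD-10 I70 alone in Denmark, France and Sweden, so hospital-coded coronary and cerebrovascular disease is not counted in main analysis item 3

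*Protocol*

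**What the plan says.** Protocol section 9.7.1, item 3, will report the share of patients with recorded risk factors, and how many each patient has, across five outcome groups that include MACE, ascertained "within 6 months prior to initiation of treatment with abrocitinib". The listed factors include "history of atherosclerotic disease, malignancy, pregnancy, history of VTE", together with age 65 or older, diabetes, major surgery and others.

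Annex 3 Table A1 supplies the codes. For history of atherosclerotic disease it gives "ICD I70.0 – I70.9" in Denmark and "ICD10 code I70" in France and Sweden. Nothing else stands in that row. The table is headed "Preliminary variable definitions in each database (subject to refinement in the SAP", and the annex adds: "Variable definitions for data from Spain (SIDIAP) and Hungary (NHIFA) will be included in the SAP".

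Table 2 in section 9.3 says this element is available from inpatient and outpatient diagnoses in Denmark and Sweden, and from inpatient diagnoses and long-term disease registration in France. Section 9.9 lists as a limitation the "potential underestimation of history of atherosclerotic disease given the likelihood of treatment within a primary care setting".

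**The concern.** The label and the code do not describe the same group. In ICD-10, I70 covers atherosclerosis of the aorta and peripheral arteries. Myocardial infarction, angina and chronic ischaemic heart disease are coded in I20-I25. Ischaemic stroke and stenosis of the precerebral and cerebral arteries are coded in I63 and I65-I66. A patient with a hospital-recorded infarction inside the lookback, and no I70 code, would be reported as having no history of atherosclerotic disease.

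Item 3 is the analysis behind the objective on consideration of risk factors, MACE included. An indicator that leaves out coronary and cerebrovascular disease under a label that appears to include them will be misread. Section 9.9 makes this worse, because it points the reader to primary-care treatment as the cause when part of the shortfall comes from the code list.

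**Working it through.** **The protocol's own figure.** Section 9.5 gives n = P(1-P)Z²/e². With P = 0.5, Z = 1.96 and e = 0.05: 0.25 × 3.8416 / 0.0025 = 384.2, rounded up to 385. This matches the text, and all nine cells of Table 3 reproduce. The present point does not depend on it.

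**Is the missing disease caught elsewhere?**
- Item 3 contains two vascular histories: atherosclerotic disease and VTE. VTE is venous, so atherosclerotic disease is the only arterial one.
- No other row of Table A1 lists ischaemic heart disease or cerebrovascular codes.
- Danish heart operations (NOMESCO group KF) appear, but under major surgery. A bypass patient scores there and not under atherosclerotic disease.
- Table 2 describes data availability by country and adds no codes.

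**Does section 9.9 explain the gap?** It names under-recording because patients are treated in primary care. Table 2 says hospital diagnoses are available in all three countries. Cases that the hospital sources do hold under other codes are dropped by the definition, which is a separate cause.

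**Direction.** Adding codes to an any-of-these-codes definition can only raise the proportion or leave it unchanged. I70 alone is a lower bound for the row.

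**Size.** The documents give no prevalence and no share with an I70 code, so both are assumed. Let T be the proportion of initiators with a qualifying record of atherosclerotic disease inside the 6-month lookback under a wider list, and s the share of those who also have an I70 code. Then observed = T × s and shortfall = T × (1 - s).

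| T | s = 0.10 | s = 0.25 | s = 0.50 | s = 0.75 |
|---|---|---|---|---|
| 2% | 0.2% (short 1.8) | 0.5% (short 1.5) | 1.0% (short 1.0) | 1.5% (short 0.5) |
| 5% | 0.5% (short 4.5) | 1.25% (short 3.75) | 2.5% (short 2.5) | 3.75% (short 1.25) |
| 10% | 1.0% (short 9.0) | 2.5% (short 7.5) | 5.0% (short 5.0) | 7.5% (short 2.5) |

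Cells show the observed proportion and the shortfall in percentage points. The shortfall runs from 0.5 to 9 points and is zero only if every such patient also carries an I70 code.

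**The other item 3 outputs.** The row adds 0 or 1 to each patient's count, so the mean number of risk factors falls by the same T × (1 - s). For the proportion with any risk factor, let a be the share of missed patients who already count through another factor, such as age 65 or older or diabetes. The shortfall is then T × (1 - s) × (1 - a), which is smaller whenever a is above zero. The documents give no value for a.

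**Precision does not repair it.** At T = 5%, s = 0.25 and n = 385, the normal-approximation half-width is 1.96 × √(0.0125 × 0.9875 / 385) = 1.11 points. The upper limit is about 2.4%, well below 5%. In milder cases, such as T = 2% with s = 0.50, whether the interval reaches T depends on the interval method, so no general statement about coverage is made.

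**The case against.** The strongest reply is that nothing is final. The table is headed preliminary, section 9.3 leaves full country-specific algorithms to the SAP, and the SAP is not at hand. That lowers the severity, and the SAP may well correct the list. It does not remove the point, because this is a stated definition that disagrees with its own label and not one left blank. Several other entries carry their own note that they are provisional: the Danish blood count and lipid codes, Swedish surgery, infections and hepatic impairment. This row has only the general heading.

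Second, section 9.9 already warns that this variable may be underestimated. The direction is indeed disclosed, but the code list is not given as a cause.

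Third, the 6-month lookback limits what any code list can find, so the gain from widening may be modest. This stands. It is why T above is defined within the lookback, and why no single capture share is offered.

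Fourth, a reader might infer that the study's principal MACE measure is wrong, or that results will look like good adherence. The documents do not support either. Item 3 is a list that is not ranked, it spans five outcome groups, and it includes age and diabetes. No threshold says what proportion would count as adherence. A low figure could be read favourably, but that is an inference about readers and not a stated decision rule.

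**Conclusion.** The point holds for Denmark, France and Sweden. Followed as written, Annex 3 understates the atherosclerotic-disease proportion and the per-patient risk-factor count in main analysis item 3, for a reason that section 9.9 does not give. The direction is certain. The size cannot be determined from the documents; the 0.5 to 9 point range rests wholly on assumed T of 2-10% and s of 0.10-0.75. The proportion with any risk factor is affected less.

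A reader might extend this to all five countries. The documents do not support that, because the Spanish and Hungarian definitions have yet to be written. Given the preliminary status of the table, this is a definition to correct before the SAP and data applications are settled. It is not a flaw in the design.

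**What to change.** In Annex 3, for Denmark, France and Sweden, widen the preliminary definition to I70 plus ischaemic heart disease (I20-I25) and ischaemic cerebrovascular and other peripheral atherosclerotic codes. Candidates are I63, I65-I66, I67.2, I73.9, and G45 without G45.4 (transient global amnesia). Study clinicians should confirm the exact list. Carry the same concept into the Spanish and Hungarian definitions in the SAP. Show I70 alone as a sub-row if that is wanted.

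Confirm that the data applications cover the added codes. Section 9.7.1 itself warns that permissions and applications may need amending when variables are added, so it should not be assumed that the current extraction suffices.

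If the list is not widened, rename the row to what I70 captures and state the code-list limitation in section 9.9 beside the primary-care one.

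The cost is a short code-list edit and a check of the data applications. Some strokes that are not atherosclerotic, such as cardioembolic ones within I63, may be included, and this should be acknowledged with the definition.

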8.2. Research objectives

The study objectives are to evaluate, to the extent measurable in the available routinely collected data, indicators of HCPs' adherence to the RMMs in accordance with the abrocitinib SmPC, prescriber's brochure and DHPC, specifically:

- Indicators of adherence to performing laboratory tests of CBC, lipid panel, hepatitis B/C and TB screening prior to initiation of abrocitinib treatment,
- Indicators of adherence to performing laboratory tests of CBC and lipid panel at week 4 (± 2 week) after initiation of abrocitinib treatment,
- Indicators of adherence to consideration of risk factors for VTE, MACE, malignancy excluding NMSC, NMSC, and serious infection prior to treatment with abrocitinib,
- Indicators of adherence to avoid live attenuated vaccines immediately prior to and during treatment with abrocitinib,
- Indicators of adherence to contraindications for use during pregnancy,
- Indicators of adherence to contraindications for use among patients with severe hepatic impairment,
- Indicators of adherence to no use in patients aged < 12 years, and
- Indicators of adherence to recommended posology (estimated average daily dose).

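### Annex 3 still defines malignancy by one code list that includes C44, although the objectives separate malignancy excluding NMSC from NMSC

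*Protocol*

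**What the plan says.** Section 8.2 of the protocol sets an objective on "consideration of risk factors for VTE, MACE, malignancy excluding NMSC, NMSC, and serious infection prior to treatment with abrocitinib". The PASS information table and the abstract use the same split. Table 2 (section 9.3) has one row labelled with both terms, "malignancy excluding NMSC, NMSC", and names a source for each of the five countries (in Spain, only if recorded in primary care). Section 9.7.1 item 3 opens by reporting "the number of risk factors for VTE, MACE, malignancy excluding NMSC, NMSC, and serious infection". The list in parentheses that follows in the same item runs "history of atherosclerotic disease, malignancy, pregnancy, history of VTE", with malignancy unsplit.

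Annex 3 Table A1 gives codes for Denmark, France and Sweden. Its group heading is "Risk factors for VTE, MACE, malignancy and serious infection", and it has one malignancy row, "ICD-10 codes C00-C75, C81-C96", to which France adds a treatment proxy where relevant. There is no NMSC row and no exclusion of C44. The table's title describes its contents as "Preliminary variable definitions in each database (subject to refinement in the SAP". Codes for Spain and Hungary are left to the SAP.

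**The concern.** Separating the two cancer elements was a deliberate change. The amendment table in section 5 gives consistency with the EU risk management plan as the reason. The code list that would turn the two names into two variables does not separate them.

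If the Annex 3 list is carried forward unchanged, patients whose only cancer code is C44 are counted under malignancy excluding NMSC, which its name rules out. The second element, NMSC, is left for each country to define. Data are prepared country by country with database-specific definitions, so an unsplit starting list could be split differently in different countries. Two reported proportions are affected, and so is the count of risk factors per patient if it is unclear whether cancer contributes one element or two.

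**Working it through.** **Inputs.**
- Code ranges C00-C75 and C81-C96: Annex 3 Table A1, malignancy row.
- Two named elements: section 8.2, Table 2, and the opening of section 9.7.1 item 3.
- C44 as the category for NMSC: the protocol does not define it. The meaning comes from the ICD-10 classification that the protocol uses.

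**Expanding the list into three-character categories.**
- C00 to C75: 76 categories.
- C81 to C96: 16 categories.
- Total: 76 + 16 = 92. C44 is one of them, because 0 ≤ 44 ≤ 75.

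**After the split.**
- Malignancy excluding NMSC: C00-C43 (44) + C45-C75 (31) + C81-C96 (16) = 91.
- NMSC: C44 (1).
- 91 + 1 = 92, so no code is lost or counted twice.

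**Direction of the error.** Let *a* be the proportion of patients with at least one of the 91 codes in the lookback window, and *b* the proportion whose only listed code is C44. The list as written reports *a* + *b* where the element's name calls for *a*. Since *b* ≥ 0, the error can only be upward. Patients with C44 and another listed cancer already belong to *a* and add nothing. The documents give neither *a* nor *b*, so the size cannot be computed.

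**Where the split appears.**

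| Place in the protocol | Malignancy split? |
|---|---|
| PASS information, abstract, section 8.2 | Yes |
| Table 2 row | Yes, both terms in one row |
| Section 9.7.1 item 3, opening | Yes |
| Section 9.7.1 item 3, list in parentheses | No |
| Annex 3 group heading | No |
| Annex 3 code row | No |

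The section 5 entry for the split lists the PASS information, sections 4, 8.2 and 9.7.1, and Table 2, but not Annex 3. This suggests how the row was missed. The inconsistency itself lies in the current text.

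**Effect on study size.** None. Section 9.5 bases its precision figures on laboratory tests. All nine entries of Table 3, including 385 at 50% and a CI width of 0.10, reproduce from the stated formula and do not depend on this code list.

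**The case against.** The strongest reply is that Annex 3 is not the operative definition. It is labelled preliminary, section 9.3 sends full country-specific algorithms to the SAP, and section 9.6 says analysis datasets follow the SAP. The row is also headed simply malignancy, so it can be read as an umbrella list from which both elements will be drawn. This lowers the severity. It does not remove the inconsistency: the protocol states a list, and that list does not match the elements its own objective names.

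Four stronger readings are tempting, and the documents do not support them.

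- *No NMSC indicator can be produced.* C44 is among the listed codes and can be subset, and Table 2 shows a source for NMSC in every country. What is missing is a separate definition.
- *The inflation can be given as a number.* If C44-only patients made up an assumed share *s* of all patients flagged by the list, the ratio would be 1/(1 − *s*): 1.25 at 20% and 1.67 at 40%. No document supports either share for abrocitinib users in a 6-month window. A share taken from cancer records in general would also ignore patients who have both C44 and another cancer, and that overlap lowers the ratio.
- *Leaving out C76-C80 loses patients with metastatic disease.* The omission may be deliberate where the source is a register of primary malignancies, as section 9.4 describes the Danish one. The question remains open where hospital or claims diagnoses are the source, as in France.
- *Item 3 contradicts itself.* The split terms there are the outcomes for which risk factors are sought. Malignancy in the parentheses can be read as one umbrella risk factor. The wording is unclear but not necessarily wrong.

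**Conclusion.** The point holds as an inconsistency between Annex 3 Table A1 and section 8.2, Table 2 and the opening of section 9.7.1 item 3. It concerns the three countries with a list in the annex; for Spain and Hungary nothing is stated that could be wrong. If the list is used unchanged, the proportion for malignancy excluding NMSC is biased upward by an unknown amount and NMSC has no definition of its own. This rests on the standard ICD-10 meaning of C44 and on the list being applied as written. Because the list is preliminary and the split needs no additional codes, this is a should-fix.

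**What to change.** - Replace the Annex 3 malignancy row with two rows: malignancy excluding NMSC = C00-C43, C45-C75, C81-C96; NMSC = C44.
- Carry the same split into the SAP code lists for all five countries.
- Align the Annex 3 group heading and the list in parentheses in section 9.7.1 item 3 with the objectives, and state whether the two count as one or two elements in the number of risk factors.
- Optionally, justify leaving out C76-C80, or add them, where hospital or claims diagnoses are the source.

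The cost is an edit to code lists and wording. The split itself needs no codes beyond those already listed, and no sample-size or precision figure changes.
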